### **1. Background and Significance**

Black individuals in the U.S. receive less effective care than White individuals for most diseases and socioeconomic and racial/ethnic disparities in chronic disease care quality are pervasive. Manifestations of structural racism, including stereotyping, prejudice and discrimination at the interpersonal level, perpetuate these disparities. Implicit bias is defined as “prejudicial attitudes and stereotypical beliefs about a particular social group” that are “activated spontaneously and effortlessly” and frequently result in discriminatory behavior. Nationwide research has repeatedly shown that the majority of non-Black physicians exhibit an implicit preference for White patients relative to Black patients when providing care, paralleling racial attitudes of the U.S. population. A study by co-I [name] et al. demonstrated associations between mild-to-moderate provider racial implicit bias and poorer communication, patient reactions and perceptions of recommended treatments. Physician bias regarding patients’ socioeconomic status (SES) has been less extensively explored, but has also been shown to impact clinical decision making. The majority of studies conducted among healthcare professionals demonstrate significant associations between higher provider implicit bias and lower quality of care.

Specifically, amongst individuals who suffer from systemic rheumatic diseases, racial, ethnic, and socioeconomic disparities have been repeatedly demonstrated. These disparities have been partially attributed to comorbidities, polypharmacy, genetics, or inadequate access to care, yet these constellation of factors do not fully explain the degree of disparities that exist. In a study of rheumatoid arthritis (RA), Black vs. White patients were more likely to receive older, conventional disease-modifying antirheumatic drugs (DMARDs) without concomitant biologics (bDMARDs), and were overall less likely to receive any bDMARDs. Lower SES individuals were

more likely to receive corticosteroid monotherapy without standard-of-care DMARDs compared with higher SES individuals. Across Brigham and Women's Hospital (BWH) and Massachusetts General Hospital (MGH), in preliminary analyses (IRB Protocol 2020P003838, Exploring bias in medication prescribing, use and referrals among patients with rheumatic and musculoskeletal conditions), among patients with gout seen in the last 2 years, Black patients were less likely to receive urate-lowering therapy (ULT) compared to White patients (43% vs. 51%) and Medicaid beneficiaries were less likely than Medicare beneficiaries (34% vs. 56%), despite minimal copayments regardless of insurance. Among RA patients, we also observed higher percentages of corticosteroid use among Black vs. White patients, and among Medicaid vs. Medicare beneficiaries, and lower percentages of concomitant methotrexate + bDMARD use among Black vs. White patients. At BWH, among 128 patients with SLE, 25% reported experiencing discrimination and high vs. low discrimination was associated, on average, with 3.5-point higher SLE disease activity scores ( $p=0.004$ ) after adjusting for age, race/ethnicity, education and insurance status (IRB Protocol 2016P000726, Understanding the role of psychosocial factors and disease activity on medication use among patients with lupus).

While patient preference and perceived discrimination during encounters have been implicated in the receipt of substandard rheumatic disease care for Black compared to White patients and for Medicaid beneficiaries, interventions that address the contribution of provider bias have not been conducted. Provider-patient communication is an important pathway by which provider implicit prejudice and stereotyping manifest, and can erode patients' trust in their providers and in the healthcare system. Most interventions to reduce provider implicit bias in the healthcare field aim to raise provider awareness of their biases with the hope that this translates into behavior change. However, research has shown that educating providers about their own implicit biases through trainings is insufficient to break prejudice or stereotyping habits, or the discriminatory behaviors that result. One intervention conducted among psychology students resulted in long-term implicit bias reduction using a "prejudice habit-breaking intervention." One component, individuation, is easily delivered within a busy clinical context, and can be incorporated into provider-patient communication, the key pathway by which bias is channeled. Individuation prevents stereotyping (a "cognitive shortcut") by obtaining specific information about members of a social group to facilitate evaluation based on personal characteristics rather than group attributes. To our knowledge, no provider-based interventions have tested individuation strategies. The goal of this pilot is to test the efficacy of an individuation-based intervention among rheumatologists and racially discordant patients at two large, multisite practices to improve racial and SES equity in receipt of high quality care. The primary aim is not to reduce provider bias, but rather to reduce the reliance on implicit bias in care decisions for Black and lower SES patients to lessen the impact of structural racism and inequality on care.

## 2. Specific Aims and Objectives

**Aim 1.** To test the efficacy of a real-time, provider-based individuation intervention to improve the receipt of high-quality rheumatic disease care among Black and lower SES individuals. *Hypothesis 1: Black and lower SES patients of providers randomized to the individuation intervention will achieve higher quality metric scores compared to patients of providers without the intervention.*

To accomplish this, providers randomized to the intervention arm will be asked to determine a set of questions that will help them uncover several unique “facts” about their patients. For example, questions about their patients’ hobbies, their daily routine, their family members (e.g., grandchildren), pets, etc. The concept behind this is that understanding these aspects that make each of their patients unique will reduce provider reliance on stereotyping. Patients actively enrolled in this study participating in Aim 2 (audiorecorded encounters), as well as other patients seen by enrolled providers who meet inclusion criteria during the study period who did not opt out of Aim 2, will all be included in de-identified chart review to examine quality of care related outcomes of interest by provider study arm.

**Aim 2.** To determine the effect of the individuation intervention on provider-patient communication, adherence, provider trust and care satisfaction. *Hypothesis 2: Providers randomized to the individuation intervention will exhibit less implicit prejudice in their communication compared to providers in the control arm; patients in the intervention arm will report greater trust, satisfaction, and adherence.*

To accomplish this, the provider-patient encounter will be audiorecorded and then aspects of communication that have previously been associated with implicit bias (e.g., physician-to-patient talk time ratio, physician word use (number of first-person pronouns, and number of positive and negative emotion-related words, divided by all words in the interaction) and total length of interaction will be assessed. In addition, surveys will be administered regarding trust, adherence and satisfaction, which have also been previously associated with implicit bias in provider-patient communication.

### **3. General Description of Study Design**

We will conduct a cluster-randomized controlled trial. The clusters are 20 rheumatologists at multisite BWH and MGH-affiliated clinics. Rheumatologists will be stratified by hospital and by gender and randomly assigned. Ten rheumatologists will be assigned to the intervention arm and ten to the control. Assessments will be conducted for 8-10 patients per rheumatologist (max 100 patients total in each arm, 200 total). Randomization will be stratified by BWH and MGH Rheumatology main campus hospitals (MGH or BWH/ Faulkner (FH)) and their rheumatology satellite clinic sites, and by provider gender (male or female). Study schema is included as an attachment.

In addition to the 200 SLE, osteoarthritis, and inflammatory arthritis patients including RA who will be studied directly, we also will examine the medical records of patients with inflammatory arthritis, osteoarthritis, or SLE in the practices of the enrolled providers seen during the same study period. In addition to the chart review of patients who meet the inclusion criteria of less than 2 visits in the past year, we will perform a secondary analysis of all patients who may have been seen greater than 2 times in the past year as we anticipate a spillover effect from the intervention and would like to study

this. Patients who were approached to participate in the audiorecorded component of the trial and declined will not be included in this medical record review. We will have no direct interaction with these patients. Most medical records we will review will be for patients of enrolled providers who we had no direct interaction with. The goal of this chart review component is to more broadly examine the impact of the intervention on the quality measures described in Table 1 below, beyond those individuals who will have their encounters audiorecorded. In addition to allowing for a larger sample size for analysis, it also will allow for analyses that may not be influenced by the act of recording an encounter (e.g., possibly, due to the recording, care may be somewhat different from other patients in each providers' practice and this will allow us to capture both). For quality metrics that would only be a onetime screen or once every few years, we will review prior records to see if they were eligible for those outcomes (such as receipt of vaccinations).

### 2. Patients

**2A. Identification:** We will identify patients with systemic lupus erythematosus, osteoarthritis, and/or inflammatory arthritis including rheumatoid arthritis, who are scheduled to see the enrolled providers from BWH/FH and MGH rheumatology main hospital clinics and their rheumatology satellite clinic sites. We will do this using a variety of methods including RPDR, EDW and EPIC searches and chart review. We will exclude any individual who has opted out of research and not contact them. Searches will be conducted by research assistants and supervised by the PI and Co-Is.

**2B. Inclusion/Exclusion Criteria:** We will include male and female patients of the participating providers who are able to provide consent, English-speaking,  $\geq 18$  years old, Black or African American or insured by Medicaid/Mass Health (as a proxy for low socioeconomic status), have a diagnosis of SLE, osteoarthritis, or inflammatory arthritis

including RA (or referred to rheumatology because of high suspicion for these conditions), and have been seen  $\leq 2$  times in the past year by the provider. In the past two years, there were  $>7,400$  patients with systemic rheumatic conditions at BWH and  $>5,600$  at MGH; 15% were Black or insured by Medicaid at BWH, 12.4% at MGH. We will exclude patients from the audiorecorded component who are incarcerated or unable to consent. We will exclude any patient from our searches who has opted out of research. If a patient declines to participate in the trial, we will not include them in the medical record review cohort either. However, if a patient of an enrolled provider does not decline participation in the audiorecorded component or is not approached for the audiorecorded component and meets our inclusion criteria, they will be included in our medical record review, along with patients who consent for participation in the audiorecorded component.

**2C. Recruitment:** Patients who did not opt out of research will be recruited directly via patient gateway and/or mailed letters sent  $\geq 1$  week before their scheduled appointment. Patients who do not opt-out will receive a phone call two days before their scheduled appointment and then again one day before their scheduled appointment (if they could not be reached 2 days before) to discuss the study and to conduct the prescreening. This will be conducted by a research assistant. If a patient has been contacted by the study staff and suggests interest in participation but cannot be consented remotely, they will be approached at the time of their visit. We will not ask for provider permission to contact each of their identified patients. We will instead ask providers to consent as part of the primary consent form to participate in the recording of the patient-provider interaction for any patient of theirs who consents to participate in the study. Since our goal is to recruit patients who are less well-established with their respective providers ( $\leq 2$  visits in the past year), providers may not know the patients well enough to determine whether they should be invited to participate. Moreover, our hope is to better understand and intervene upon potential provider bias and by asking providers to select which patients should/should not participate, we would be introducing additional bias and may exclude patients at risk for experiencing the greatest degree of bias.

The PI will conduct ongoing monitoring of patient responses to ensure that the selection criteria are identifying the right patients. All complaints about this method of recruitment will be submitted to the IRB as an other event.

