(<https://stanford.cloud-cme.com/course/courseoverview?P=8&EID=20775>). This module has been approved by the MA Medical Society and is eligible for CME, which can be applied towards the unconscious bias training CMEs required for MA medical license renewal as of June 1, 2022. Upon completion of the unconscious bias module, providers in the intervention arm will meet with study team members to discuss their “individuation” countermeasure intervention and to view the brief presentation with a study team member about individuation. Providers will be given a choice of several individuation-related questions: “How do you spend a typical weekend day?”, “How do you spend a typical weekday?”, “What is your priority related to your health?”, “What are your hobbies/things you enjoy to do in your free time?” and “Can you describe something about yourself that you think makes you unique/different from other people?” to better understand the unique characteristics of each patient. The goal is that this will overcome the physicians unconscious stereotyping and allow them to see each patient as an individual as opposed to as a member of a certain racial or socioeconomic group. Once the provider decides on his/her choice phrases from the above list, the research team will assist with the development of a smart phrase (also called “dot phrase”) to allow them to incorporate this into a note. Once a week, providers in the intervention arm will receive an email reminding them to incorporate this question and the documentation into their clinic notes (see attachment of “Provider Reminder Email Script.”). We do not anticipate that these questions will include any answers that will place the research subjects at risk, but rather will allow their provider to get to know them better. This documentation will both allow for providers to be reminded of these individual characteristics at a later visit, and also allow the study team to review the notes to determine uptake of the intervention.

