#### 4. Return of results

For providers, all data will be deidentified and analyzed in aggregate. Unique de-identified codes will be used for the provider IATs that will be linked with the provider-patient recordings. The PI and Co-Is will be blinded and only see de-identified data which will be used for analyses. This is to reduce any risk to the providers reputation or employment. One experienced, trained research assistant will be able to link the data to identifiers should an unexpected situation arise and make this necessary however the PI and Co-Is will be blinded in order to ensure that the reputation of providers in their practices is preserved. Results in aggregate will be presented in an end-of-study Grand Rounds to both the BWH and MGH rheumatology divisions (there is a combined grand rounds). The title of this grand round will be “Presentation of Findings from Breaking Implicit Bias Habits Intervention Study.” We will submit this presentation to the IRB for approval prior to the Grand Rounds. If we do find examples of implicit bias and explicit discrimination, we will work with MGB equity leadership in this area, who are aware of this study and have been part of these discussions (including [name], [name] and [name]) to determine the best Division-wide training tools to use to address this need.

For patients, data will also be de-identified for analyses and de-identified codes will link survey responses with the provider-patient encounter. However, we will be able to link survey scores back to patients and after the completion of the 3-month adherence study, we will provide them with a score report indicating what their scores on each of the respective surveys mean. A sample score report will be submitted as an amendment once we have analyzed surveys and have determined the best way to present these data.

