## 9. Statistical Analysis

Power calculations are based on Aim 1's primary outcome (quality metric score). We account for an intracluster correlation coefficient (ICC) of 0.02 among patients of the same provider and assume a two-sided alpha level of 0.05. With 10 providers in each arm (N=20) and 8 patients per provider (N=160), we would have 84% power to detect a mean difference between arms of 0.5SD. If the ICC is 0.05, we would have 84% power to detect the same mean difference if 10 patients per provider were included.

All analyses will follow intention-to-treat (ITT) principles. All analyses will follow intention-to-treat (ITT) principles. For Aim 1, unadjusted and adjusted linear generalized estimating equation (GEE) models that account for patient clustering by providers will be used, with the quality metric score as the primary dependent variable, intervention arm as the primary predictor variable and covariates including hospital, and other factors that are either strongly correlated with the dependent variable (e.g. rheumatic disease) or imbalanced between the arms. We will use Millisecond software to program the IATs and calculate D scores that reflect response times and compare these findings across the two groups. For Aim 2, unadjusted and adjusted linear GEE models will be constructed with a) communication metrics and b) models for each survey score as the dependent variables, intervention arm as the primary predictor variable, and covariates as above. We will also analyze the transcripts qualitatively using Dedoose software and use the constant comparison method to evaluate and refine our themes and our codes.

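### Patients are recruited after their provider is randomised, by research assistants not stated to be masked and with no fixed approach order; this exposes mainly the Aim 2 recorded sample, and the primary score less so, to selection bias

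*Combined protocol and SAP*

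**What the plan says.** - **Order of events.** Section 5 has providers randomised once they agree to participate. Section 6 (Providers) starts recording at least one month after the implicit association tests, with 8-10 encounters per provider.
- **Who recruits.** Section 4 (2A) gives the patient searches to research assistants, supervised by the PI and Co-Is. Under 2C, patients who have not opted out are phoned two days before the appointment, and again the day before if not reached, "to discuss the study and to conduct the prescreening. This will be conducted by a research assistant".
- **Who is masked.** Section 6 (Return of results) says: "The PI and Co-Is will be blinded and only see de-identified data which will be used for analyses". The purpose given is to protect providers' reputation and employment. Research assistants are not covered.
- **Who delivers the intervention.** Under Section 6 (Providers), study team members hold the individuation meeting, "the research team will assist with the development of a smart phrase", and intervention providers get a weekly reminder email. These tasks are not stated to be kept apart from recruitment.
- **What happens to decliners.** Section 4 (2B) states: "If a patient declines to participate in the trial, we will not include them in the medical record review cohort either". Section 3 and Section 6 (Chart reviews) agree. Patients never approached, or sent a letter but not reached, can stay in.
- **Where the primary score is measured.** Section 6 (Outcomes) uses the wider chart-review cohort, with recorded patients as a separate subgroup. Section 9 states intention-to-treat without addressing decliners.

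**The concern.** Randomising providers balances the providers and, in expectation, the patients they would see anyway. It does not protect the choice of which of those patients enter the study afterwards. If the person searching and calling knows the arm, effort and persuasion can differ by arm, and so can the order of approach.

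Aim 2 (communication measures, trust, satisfaction and other survey scores) rests wholly on patients who were approached, consented and were recorded, so any such difference enters its comparison directly. Providers can also opt out of a given recording just before the visit.

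The primary score is reached by a narrower route. An approached patient who refuses leaves the chart-review cohort, while a patient who was never approached stays. Being approached therefore decides who can be removed after randomisation.

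The plan sees part of this hazard. Section 4 (2C) keeps providers from choosing patients because that could leave out those at greatest risk of bias. Section 5 records demographics when a provider opts out of a recording. Neither safeguard is extended to recruiters or to patients who decline.

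**Working it through.** **1. The plan's own figure.** Section 9 takes an "intracluster correlation coefficient (ICC) of 0.02 among patients of the same provider", asks the reader to "assume a two-sided alpha level of 0.05", and states: "With 10 providers in each arm (N=20) and 8 patients per provider (N=160), we would have 84% power". The target for that power is a difference of 0.5 SD in the mean quality score.

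- Design effect = 1 + (8 − 1) × 0.02 = 1.14; effective n per arm = 80 / 1.14 = 70.2; normal-approximation power = 84.2%.
- Second scenario (ICC 0.05, 10 per provider): design effect = 1 + 9 × 0.05 = 1.45; effective n = 100 / 1.45 = 69.0; power = 83.6%.

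Both match the stated 84%. The power statement is not in dispute. It is needed here for the standard error: SE = √(2 × 1.14 / 80) = 0.169 SD.

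**2. Bias from removing decliners (primary score).** Let p be the share of an arm's chart-review cohort removed as decliners, and g the mean score of retained patients minus that of decliners, in SD. The arm's full mean is (1 − p) × retained + p × decliner, so removal shifts the arm's mean by p × g. The shift in the arm comparison is p₁g₁ − p₀g₀. It is zero when p and g are the same in both arms. With a common g it is (p₁ − p₀) × g.

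**3. Illustration.** The differences in share and the score gaps below are assumed; the documents give neither.

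| Arm difference in share removed | g = 0.25 SD | g = 0.5 SD | g = 1.0 SD |
|---|---|---|---|
| 0 points | 0 | 0 | 0 |
| 5 points | 0.0125 SD | 0.025 SD | 0.05 SD |
| 10 points | 0.025 SD | 0.05 SD | 0.10 SD |
| 20 points | 0.05 SD | 0.10 SD | 0.20 SD |

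With equal arms, the difference in share cannot exceed twice the average share, so the 20-point row needs an average loss of at least 10%.

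**4. Effect on the two-sided 5% error rate**, from a normal test statistic centred at bias / SE:

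| Bias | 8 per provider, ICC 0.02 (SE 0.169) | 24 per provider (assumed), ICC 0.02 (SE 0.110) |
|---|---|---|
| 0.025 SD | 5.3% | 5.6% |
| 0.05 SD | 6.0% | 7.4% |
| 0.10 SD | 9.1% | 14.8% |
| 0.20 SD | 22.0% | 44.2% |

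The second SE is √(2 × 1.46 / 240), with 1.46 = 1 + 23 × 0.02. A larger chart-review cohort shrinks the SE but not a given bias.

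**5. Number of decliners.** To record n patients at acceptance a, n/a − n decline. For n = 160 to 200 this is 28-35 at 85%, 69-86 at 70% and 160-200 at 50%. The 85% is what Section 7 quotes from an earlier videotaping study; the other rates are assumed.

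**6. Aim 2.** The identity in step 2 applies, with p now the share of eligible patients not recorded for any reason (not approached, not reached, declined, or provider opt-out) and g the gap between recorded and unrecorded patients. This p contains the decliners and more besides. Even if p is equal in both arms, a different choice of patients makes g differ and biases the comparison. That is why Aim 2 carries most of the exposure.

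**The case against.** **Contact is already tied to the appointment.** Section 4 (2C) sets a routine of letter, call two days before and call one day before. Read literally, it covers every identified patient who has not opted out, which is close to consecutive approach. This stands in part. However, recording stops at 8-10 per provider, Section 3 expects most reviewed charts to belong to patients with no study contact, and no rule says who is approached when slots are limited.

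**The criteria leave little to judgement.** A reader might infer that a research assistant decides who has a high suspicion of disease. The text does not support that: in 2B the phrase describes why the patient was referred. The other criteria are mostly record-based.

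**Other safeguards exist.** Providers do not choose who is contacted, and patients are not told the details of the intervention, so refusal that depends on arm would have to come mainly from recruiter behaviour. The prescreening script and Manual of Operating Procedures are not among the documents and may separate the tasks.

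**A surplus of patients cannot be shown.** A reader might take the counts in 2B (0.15 × 7,400 + 0.124 × 5,600 = 1,804, or about 24 per rheumatologist across 74) as proof of ample room to choose. Those are two-year counts, while recruitment is estimated at 6 months. A simple quarter is about 6, and the language and visit limits come on top. At 85% acceptance, 8-10 recordings need about 9-12 approaches.

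**Nor can a share removed be fixed.** Setting 35 decliners against 20 × 24.4 = 488 charts gives 7%. A quarter of that pool (122) gives 29%. All patients with the listed diseases, without the Black or Medicaid limit (13,000 / 74 × 20 = 3,514), gives 1%. None of these is usable as an estimate.

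**Excluding people who refused may be required.** Agreed. The remedy does not use their charts.

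**Conclusion.** The point holds as a design weakness with a cheap remedy. Recruitment follows allocation, the documents do not mask the recruiters, and no approach order is fixed. Aim 2 is the main exposure.

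The primary score is exposed to a smaller extent. A reader might infer that deleting decliners biases it by itself; it does not. Equal loss with an equal score gap in both arms narrows the population but leaves the comparison unbiased. Bias needs the decline share, or the gap, to differ by arm.

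The documents fix neither size nor direction. Under the assumed inputs above, a 5-point difference with a 0.5 SD gap is minor (0.025 SD, error rate 5.3-5.6%). A 20-point difference with the same gap is not (0.10 SD, error rate 9.1-14.8%), but it requires substantial refusal. These figures rest on a common score gap, equal arms and the normal approximation. They show scale and are not predictions.

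**What to change.** In Section 4 (2A to 2C):

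1. Draw each provider's eligible list from RPDR, EDW and Epic without the allocation.
2. Approach eligible patients consecutively by scheduled appointment until 8-10 are recorded.
3. Assign the calls and prescreening to an existing research assistant who does not hold the allocation and takes no part in individuation meetings, smart-phrase building or reminder emails.
4. Log the numbers eligible, approached and declined by provider and arm, and report them.

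Decliners' charts stay excluded as now. If the operating manual already provides for any of this, the protocol should say so.

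The cost is a division of tasks among existing staff and slightly less flexibility in filling recording slots. Section 4 refers to research assistants in the plural but does not give their number, so the sponsor should confirm that the split is workable. No patient procedure is added.
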